Figure 4 is based upon a simplified 2-group comparison (e.g., with **X** as an indicator of treatment assignment to BA over ST). In reality, treatment assignment will be coded using three contrasts corresponding to the main effects of the psychological and pharmacological treatment components and their interaction, so as to accommodate the hypothesized moderation of the path between hedonic capacity and cigarette reward value by varenicline (Preacher, Rucker, & Hayes, 2007). Simultaneous estimation of the effect of multiple mediators (e.g., hedonic capacity and cognition) will be conducted as in Napolitano et al (2008). Once mediation of the intermediate outcome (cigarette reward value) has been modeled as described above, we will estimate the remaining paths linking intermediate outcomes (cigarette reward value, craving/withdrawal) to the distal outcome (abstinence) via logistic regression. Although we see value in building the model in a piecewise fashion (e.g., in terms of evaluating the need to adjust for potential confounders of the treatment to outcome relationship), we will also estimate the full model in Figure 2 in a single step using the structural equation modeling (SEM) package Mplus 6.0 (Muthén & Muthén, 1998-2010), which allows the user to assess the statistical significance of any complete mediation path via bootstrapping. One important consideration is the choice of measurement points at which to assess the mediators to maximize intervention effects while also preserving the temporal precedence between mediator and outcome. Because all putative mediators follow an intensive measurement schedule, we will be able to estimate their longitudinal trajectories precisely, and will identify appropriate turning points at which the treatment effect is maximized.

RETAIN Sub-Study Analyses

Randomization

Participants will be randomized to the 3 experimental arms (\$0, \$200, \$500) in equal, 33.3% probabilities. A Penn analyst will use the REDCap randomization module to implement block randomization stratified by phone screeners across the two sites. The trial's primary statistician on the Penn research staff will create a block randomization scheme for each screener and will upload a CSV file of each block assignment to the REDCap randomization module. The screener will select his or her name via the REDCap software through an initialization step and will immediately receive the randomization assignment for that participant. This will allow the screener to immediately present the participant with the correct incentive amount, and subsequently present the correct paper informed consent form at the intake visit.

Analytic Strategy

In Secondary Aims 2 and 2a of the trial, we will assess bivariate relationships of incentives with the outcomes described above using t-tests or Wilcoxon rank-sum tests for normally and non-normally distributed continuous variables, and chi-square tests for comparisons of proportions. To examine the hypothesized statistical interactions, we will use logistic, linear, or quantile regression, as appropriate based on outcome

parameterizations and distributions. For all outcomes other than tests for undue or unjust inducement, we will adjust significance levels for multiple comparisons using the Sidak-Holm method.

In all analyses, we will model the center from which patients are recruited as a fixed effect, thereby mitigating confounding by center and adjusting variance estimates for clustering of participants within centers. To adjust for chance covariate imbalance among arms, we will include covariates in multivariable models if they are significantly associated with the intervention arm and predictive of enrollment in the smoking cessation study in bivariate analyses. We will explore temporal trends in incentives' effects over the study period using stratified analyses. If temporal trends are noted, as may occur if prospective patients learn of the incentives study, we will adjust for their influence by entering time as a covariate, modeled as a spline.

Our analyses to rule out undue and unjust inducements entail three primary covariates. All models will have the primary outcome of enrollment in the parent RCT as the outcome. First, to determine whether incentives represent undue inducements for research participation, we will test the statistical interaction between incentive size and the primary covariate of risk perception on the outcome of enrollment in the parent RCT. Second, to determine whether incentives represent unjust inducements for research participation, we will test two interactions, each in a separate model to avoid collinearity: that between incentive size and the primary covariate of annual household income, and that between incentive size and the primary covariate of economic well-being.

Analyses of these interaction terms will be structured as tests of non-inferiority, such that the null hypotheses are that incentives do meet criteria for undue or unjust inducement, and we reject the null, and conclude the absence of undue or unjust inducement, if the interaction terms are "small" according to pre-specified criteria (in technical terms, the inferiority margin). Said a different way, our analyses are designed to determine whether we can exclude the possibility that incentives represent undue or unjust inducements if the resulting interaction terms are sufficiently small. Specifically, we will use one-sided alpha levels of 0.05 to exclude, with 95% confidence, the possibility that any of these interaction odds ratios are >2.0 .

Secondary Aim 2b explores the incremental cost-effectiveness of using research incentives to recruit a fixed sample size from the perspective of the research sponsor and investigators. We define the incremental cost-effectiveness ratio (ICER) as the incremental costs of conducting the trial with vs. without a given incentive (or with one incentive vs. another), divided by the time saved in the presence of the incentive or larger incentive. We will evaluate 3 specific ICERs: (i) \$500 vs. \$0, (ii) \$200 vs. \$0, and \$200 vs. \$500. Relevant costs to be analyzed include the total costs of the incentives themselves (the incentive amount multiplied by the number of patients receiving it) and the costs of conducting the RCT for sufficiently long to recruit that number of patients. These latter costs include, for example, the costs of direct recruitment activities such as mailings, advertisements, and phone charges, and the duration of salary and benefits support needed for relevant study personnel.

CONFIDENTIALITY

All participant information will be kept in a secure filing cabinet that is accessible only to authorized study personnel. All databases containing participant information will be password protected, and again, accessible only to authorized study personnel on NU's password-protected and encrypted network. Prior to access to any study-related information, personnel will be required to sign statements agreeing to protect the security and confidentiality of identifiable information. Each participant will have a unique study ID number for all data collected. In all datasets, we will use ID numbers only. A separate data set linking names with ID numbers will be accessible only by the study biostatistician. All communications about participants will use the ID number only and never include names or other personal information. All data will be stored until all analyses are completed. No data will be shared with any unauthorized party (i.e., aside from study personnel and regulatory officials). Any publication of data will not identify subjects by name or with an identifier that could be used to reveal identity. Data will be accessible to the study PIs (lead and PENN site PI), co-investigators, the study physician, other study staff, and the Northwestern and PENN IRBs and their Offices of Human Research.

Protected Health Information (PHI)

The following PHI will be collected as part of this study:

- Name, address, telephone number
- Email address
- Date of birth
- Social Security Number (PENN site only)
- Some personal information that may be considered sensitive, such as medical history, psychological history, alcohol and other substance use history, etc.
- Results from physical examinations, tests or procedures
- Medical record number

Precautions, as described above, will be taken to ensure that the privacy of subjects' personal health information will be maintained.

PARTICIPANT COMPENSATION

Main Trial

Participants will be compensated for their time up to a maximum of \$140 (see Table 5). Participants will also be reimbursed for transportation expenses related to their participation in the study with \$10 for each clinic visit (up to \$60). The Northwestern site will provide compensation in cash for all sessions (except the Week 27 phone session). The PENN site will provide compensation in cash at the intake visit, but all other visits will be compensated using a Greenphire ClinCard, which is a reloadable, pre-paid card. Compensation will be loaded onto the ClinCard at the end of successfully completed visits. Participants will be issued the ClinCard at Pre-Quit 1. Participants at the Northwestern site will receive compensation for achieved phone sessions at the next clinic visit, and participants at the PENN site will receive compensation within 24 hours of an achieved phone session on the ClinCard. Participants who complete the week 27 phone session but report that they are currently smoking will not be eligible to come in for the week 27 clinic visit. To reimburse these participants for completing the week 27 phone session at the Northwestern site, an electronic gift card to the retailer of their choice (e.g., Target, Walmart, Amazon.com) will be sent to the participant's email and activated through the e-voucher link provided in the email. To reimburse these participants at the PENN site, \$10 will be loaded onto the ClinCard.

Table 4. Participant Compensation

Study Session	Session	Travel/Parking
Intake Session (Week 0)	\$15	\$10
Week 1 (Pre-Quit 1; Clinic)	\$15	\$10
Week 2 (Pre-Quit 2; Phone)	- (No assessment)	-
Week 3 (Target Quit Day)	\$10	\$10
Week 4 (Phone)	\$10	-
Week 6 (Phone)	\$10	-
Week 7 (Clinic)	\$15	\$10
Week 8 (Phone)	\$10	-
Week 10 (Phone)	\$10	-
Week 12 (Phone)	\$10	-
Week 14 (Clinic)	\$15	\$10
Week 27 (Phone)	\$10	
Week 27 (Clinic)	\$10	\$10
	\$140	\$60

Total: \$ 200

RETAIN Sub-Study

Participants who are eligible for the RETAIN sub-study at phone screen but are not enrolled in the main trial will not receive any RETAIN sub-study compensation. Participants who complete all RETAIN sub-study

procedures will receive two installments of \$150 each following the Intake and Week 27 study sessions, for a total payment of \$300. This payment will be made in the form of a stored value payment card, with oversight from the Penn RETAIN study team. During the debriefing session, research staff will explain that all RETAIN sub-study participants receive a \$300 payment, regardless of what was stated in the Informed Consent Form.

INFORMED CONSENT

Main Trial

Fully trained research personnel will obtain informed consent using the combined consent and HIPAA form approved by the Northwestern and PENN IRBs. The consent process will take place before study data are collected and prior to any treatment. Consenting will occur in person at the start of the intake session and will involve a one-on-one discussion of the study requirements and procedures and an opportunity for participants to ask questions and express concerns. The participants will receive a copy of the combined consent and HIPAA form for their records. In addition, the participants will be given the PI and study physician's contact information should they wish to speak to either of them during the course of the study regarding their consent or the study procedures. The consent process will take place in English, there will be no waiting period, no coercion to participate, and all participants will be considered competent to provide informed consent (i.e., they will be asked if they understand to what they are consenting).

RESOURCES AND STUDY MANAGEMENT FOR HUMAN SUBJECTS PROTECTION

Qualifications of PIs

[name]. (Lead PI, Northwestern University)

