Mediators/ moderators: 1) *Income and personal financial wellbeing*. Annual household income will be assessed using a 6-level variable. Participants' economic wellbeing (e.g., whether participants have recently borrowed money to "make ends meet") will also be assessed. 2) *Participant characteristics*. Other factors that may influence response to financial assessments will be assessed; including prior research participation, age, race, gender, ethnicity, education, and marital status; with items taken from main trial demographic forms where possible.

Main outcome: Proportion of participants assigned to each incentive amount who consent to participate in the main trial.

Secondary outcomes: 1) Attention to Informed Consent Document (i.e., time spent reading each section, as described in Procedures above). 2) Research Attitudes Questionnaire (Kim, Kim, McCallum, & Tariot, 2005). 3) Perceived research risk (Cryder, London, [name], & Loewenstein, 2010). 4) Therapeutic misconceptions (S. L. Kim SH, Wilson RM, Frank SA, Holloway RG, Keiburtz K, De Vries RG, 2009; W. R. Kim SH, De Vries R, Kim H, Holloway R, Kieburz K, 2015; Pentz et al., 2012). 5) Trial Elements Quiz (S D [name], 2002; S D [name], [name], Casarett, Berlin, & Asch, 2004). 6) Perceived Coercion Scale (Gardner W et al., 1993). 7) Study retention (i.e., proportion of participants assigned to each incentive amount who complete study procedures through week 27).

RISK/BENEFIT ASSESSMENT

Potential Study Risks

A detailed description of the study will be given to all participants, which will include the risks of participation, assurance of full confidentiality, and the knowledge that their freedom to refuse participation or withdraw from the project will not affect the availability of treatment at Northwestern or PENN. Informed consent procedures will comply with current standards of the IRBs at Northwestern and PENN. Participants can choose, as an

alternative, to not enroll in this study. Adverse reactions will be assessed and reported as required by Federal law and the regulations of Northwestern and PENN. Potential study-related risks are listed below.

Mild Emotional Distress in Response to Assessments or Therapy

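### RETAIN randomisation is blocked within phone screener, but no RETAIN analysis names screener as a term, so the incentive comparisons may be mildly conservative

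*Combined protocol and SAP*

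**What the plan says.** All of this is in the combined protocol and SAP, mainly under RETAIN Sub-Study Analyses.

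- **Randomization.** The three offers ($0, $200, $500) are allocated "in equal, 33.3% probabilities". The scheme is "block randomization stratified by phone screeners across the two sites", and the statistician "will create a block randomization scheme for each screener". Screeners pick their own name in REDCap and receive the assignment at once. They then present the offer by phone and the matching consent form at intake.
- **Analytic Strategy, standing adjustment.** "In all analyses, we will model the center from which patients are recruited as a fixed effect". The reasons given are confounding by centre and clustering within centre.
- **Analytic Strategy, conditional adjustment.** Covariates enter "if they are significantly associated with the intervention arm and predictive of enrollment" in bivariate analyses. If time trends are seen, "we will adjust for their influence by entering time as a covariate, modeled as a spline".
- **Analytic Strategy, tests.** Proportions are compared with chi-square tests. Interactions use logistic, linear or quantile regression. The undue and unjust inducement tests are non-inferiority tests at one-sided 0.05 that seek to exclude interaction odds ratios above 2.0.
- **RETAIN Sub-Study Measures.** The main outcome is "Proportion of participants assigned to each incentive amount who consent to participate in the main trial".

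Screener does not appear as a term in any of these analyses.

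**The concern.** Screener is the randomisation stratum, and centre is a coarser grouping of it. Blocking within screener makes the arms nearly balanced on screener, so screener differences in enrolment largely cancel out of the arm comparison. An analysis that omits screener still counts those differences as noise. Its standard error is then too large for the design that was run, its true type I error falls below nominal, and some power is lost.

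Screener could plausibly matter here, because the person who delivers the offer may influence whether the caller goes on to enrol. The plan's clustering argument for centre applies equally to screeners within a centre. What is at stake is modest: some precision on the RETAIN main outcome, and clarity about which odds ratio the inducement margin refers to.

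**Working it through.** **No planned figure to reproduce.** The documents give no RETAIN sample size, power, expected enrolment fraction, number of screeners, block size or screener variance. Everything numerical below rests on stated assumptions.

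**Step 1: do the other rules bring screener in?**
- The covariate rule needs two things: association with arm and prediction of enrolment. Equal allocation in blocks within each screener makes the first close to impossible beyond incomplete final blocks, however strongly screener predicts enrolment.
- The spline concerns calendar time.
- The chi-square test has no strata.

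So the gap is real.

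**Step 2: analytic size.** Let ICC be the within-centre screener intraclass correlation of enrolment. With balanced blocking, the true variance of the arm difference is (1 − ICC) times the variance that a screener-omitting model uses. For an assumed two-sided 0.05 test (the plan gives no base alpha for these outcomes):

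- effective critical value c = 1.960 × √(1/(1 − ICC))
- actual alpha = 2 × (1 − Φ(c))
- power without screener = Φ(1.960 + z − c), where z = 0.842 for 80% adjusted power and 1.282 for 90%

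Example, ICC 0.05: c = 1.960 × 1.0260 = 2.011; alpha = 0.0443; power = Φ(1.960 + 0.842 − 2.011) = Φ(0.791) = 78.5%.

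| Assumed ICC | c | Actual alpha | Power, from 80% | Power, from 90% |
|---|---|---|---|---|
| 0 | 1.960 | 0.0500 | 80.0% | 90.0% |
| 0.01 | 1.970 | 0.0489 | 79.7% | 89.8% |
| 0.02 | 1.980 | 0.0477 | 79.4% | 89.7% |
| 0.05 | 2.011 | 0.0443 | 78.5% | 89.1% |
| 0.10 | 2.066 | 0.0388 | 76.9% | 88.0% |
| 0.15 | 2.126 | 0.0335 | 75.0% | 86.8% |

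**Step 3: what these ICCs mean.** With mean enrolment near 31%, a screener SD of 0.5 on the logit scale gives an ICC of about 0.05, and the 10th to 90th percentile of screener enrolment rates is 18% to 45%. An SD of 0.75 (mean about 32%) gives an ICC of about 0.10 and a spread of 14% to 53%. These are already large differences between people making the same offer.

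**Step 4: simulation check.** Logistic regression, $500 versus $0, 4,000 runs per scenario. Assumed: 576 people screened (the main trial's total, used as a placeholder), 8 screeners in 2 centres, blocks of 6, baseline logit −0.4, log odds ratio 0.58 for $500 and half that for $200.

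| Screener logit SD | Power, centre only | Power, screener added | Difference (points) | Type I error, centre only / screener added |
|---|---|---|---|---|
| 0.25 | 78.95% | 80.50% | 1.55 | 4.5% / 4.9% |
| 0.5 | 77.28% | 79.45% | 2.17 | 5.2% / 5.7% |
| 1.0 (extreme) | 67.63% | 73.25% | 5.62 | 3.7% / 5.0% |

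The Monte Carlo standard error is about √(0.79 × 0.21/4,000) = 0.6 points for the power figures and √(0.05 × 0.95/4,000) = 0.3 points for type I error. The direction agrees with Step 2: centre-only power and type I error are the lower in every row. The type I error differences in the first two rows are about the size of that error.

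**The case against.** The case for leaving the plan alone has force.

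- **Nothing shows that screener predicts enrolment.** Enrolment also depends on later steps: an intake visit up to 60 days after screening, a consent discussion and final eligibility checks. If screeners do not differ, the loss is zero. This stands, and it is why the point is conditional.
- **The planned adjustment is more than centre.** There are conditional covariates, a possible time spline and chi-square tests. A reader might infer that centre is the only adjustment ever made, and the text does not support that. Centre is the only adjustment always made, and none of the others names screener.
- **Screener effects have a price.** Recruitment was planned over 48 months, and low-volume screeners would give sparse strata. This stands as a reason for a pooling rule, a random effect or a stratified test, but not for omitting the stratum.
- **Conditioning changes the odds ratio.** A shift towards 1 when screener is omitted reflects non-collapsibility: the marginal and screener-conditional odds ratios are different quantities. This stands, and a difference in proportions is not affected.

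Two stronger readings are tempting. One is that RETAIN has a known, material loss of power; without a sample size, power target or screener variance, the documents cannot support that. The other is that the inducement tests become anti-conservative, because an interaction odds ratio pulled towards 1 moves away from the 2.0 margin. That follows only if the margin is meant conditionally on screener. The plan does not say, so what it shows is an unspecified margin and not an inflated error rate.

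**Conclusion.** The mismatch between randomisation and analysis is real and minor. The consequence for the incentive comparisons is mild conservatism, not confounding bias or inflated type I error, since screener is balanced by design.

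The loss of about 0.3 to 3 points assumes ICC 0.01 to 0.10, 80% adjusted power, a two-sided 0.05 test and near-complete blocks. It reaches 5 points at ICC 0.15. RETAIN serves Secondary Aims 2 to 2b, and no stated power figure is contradicted. The case for acting rests on the low cost and on analysing as randomised, not on the size of the loss.

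**What to change.** Amend the RETAIN Analytic Strategy before arm-level enrolment data are examined:

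1. **Models.** Include screener, nested in centre, as a stratification term in the RETAIN enrolment analyses whether or not it meets the covariate rule. Use either a fixed effect with a stated rule for pooling low-volume screeners within a centre, or a random effect. Choose one in advance and set the pooling threshold from call volume, not from results.
2. **Main enrolment comparison.** Replace the unstratified chi-square with a Cochran-Mantel-Haenszel test stratified by screener. It tolerates small strata, and the plan already uses this kind of weighting for adverse events.
3. **Inducement tests.** State that the interaction odds ratio margin of 2.0 applies to the screener-adjusted model, because conditional and marginal odds ratios differ.

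If the team prefers centre alone, it should say why.

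The cost is a few more model parameters and one pooling rule. No new data should be needed, because the screener's name is selected at randomisation in REDCap. Initial Eligibility Screening, however, describes RETAIN randomisation as running through the main trial's data management system, so the team should confirm that screener identity is kept in the analysis file.

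### RETAIN's covariate screen on randomized incentive arms leaves out strong predictors of enrollment about 95% of the time and lets chance choose the model

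*Combined protocol and SAP*

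**What the plan says.** The rule is in RETAIN Sub-Study Analyses, Analytic Strategy. Its stated purpose is "To adjust for chance covariate imbalance among arms". Covariates are added to multivariable models "if they are significantly associated with the intervention arm and predictive of enrollment in the smoking cessation study in bivariate analyses". Both conditions must hold, and both are judged on the sub-study's own data. No covariate list and no significance threshold are given for the rule.

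Other terms do not depend on it:

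- Center is always present: "we will model the center from which patients are recruited as a fixed effect".
- Time is conditional. If trends are noted, "we will adjust for their influence by entering time as a covariate, modeled as a spline".
- The inducement models have fixed terms of their own ("Our analyses to rule out undue and unjust inducements entail three primary covariates"): risk perception, household income and economic well-being. The last two are placed in separate models to avoid collinearity.

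The Randomization paragraph says "Participants will be randomized to the 3 experimental arms" with equal probability, using "block randomization stratified by phone screeners across the two sites". The screener is not named as a model term.

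RETAIN Sub-Study Measures lists candidate characteristics, "including prior research participation, age, race, gender, ethnicity, education, and marital status", besides household income and economic well-being. Initial Eligibility Screening says that randomized callers are told their incentive condition at once. It also says that they answer phone questionnaires on demographics and finances, research attitudes, previous research experience and perceived risk.

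**The concern.** Testing a baseline characteristic against a randomized arm tests something already known to be due to chance. The test says nothing about how much that characteristic matters for enrollment, which is what makes adjustment worthwhile. A strong predictor that happens to be balanced is left out, and the condition on predicting enrollment cannot bring it back, because both conditions are required.

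Two things are at stake. One is power for the incentive effect on enrollment. The other is knowing in advance which quantity will be estimated. Odds ratios are non-collapsible, so the conditional odds ratio depends on which predictors of enrollment are in the model. If the rule is applied to the inducement models, chance also helps decide which interaction odds ratio is compared with the margin of 2.0.

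**Working it through.** The plan gives no sample size, power or threshold for this rule, so there is no figure to reproduce. What follows illustrates its consequences.

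**1. Chance of passing the arm condition.** Assume a 0.05 threshold. Under valid randomization a baseline covariate is significantly associated with arm with probability 0.05, however strongly it predicts enrollment. It is omitted with probability 1 − 0.05 = 0.95.

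**2. Chance that at least one candidate is flagged as imbalanced.** With k independent candidates this is 1 − 0.95^k.

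- k = 7 (the listed characteristics): 1 − 0.95^7 = 30%.
- k = 9 (adding household income and economic well-being): 1 − 0.95^9 = 37%.

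These figures cover the arm condition alone. The chance that the model changes is lower unless every candidate also predicts enrollment.

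**3. Effect on power and type I error.** Simulation, 2,000 data sets per scenario: three equal arms, binary enrollment, logistic model, 2-df likelihood-ratio test of incentive, and one standard-normal prognostic covariate. None of the following is in the documents: N of 300, 600 or 1,200; intercept −0.8; incentive log odds ratios 0.25 and 0.5 for the two higher arms; covariate log odds ratio 0.7 or 1.2 per SD; threshold 0.05 for both conditions. The three strategies were applied to the same data sets.

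| N | Covariate log-OR | Power: no adjustment | Power: plan's rule | Power: pre-specified | Gain over rule (points) |
|---|---|---|---|---|---|
| 300 | 0.7 | 25.4% | 25.6% | 28.2% | 2.6 |
| 600 | 0.7 | 47.9% | 48.1% | 50.7% | 2.6 |
| 1,200 | 0.7 | 79.8% | 80.0% | 83.9% | 3.9 |
| 300 | 1.2 | 23.4% | 22.6% | 27.8% | 5.2 |
| 600 | 1.2 | 37.8% | 38.4% | 47.7% | 9.3 |
| 1,200 | 1.2 | 66.7% | 67.0% | 78.4% | 11.4 |

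- The covariate met the enrollment condition in essentially every data set, yet the rule included it in only 4.0% to 5.8% of them.
- The rule's power was within 1 point of no adjustment in every row.
- With no incentive effect, rejection rates were 4.0% to 6.0% across all strategies and scenarios, and 4.0% to 5.6% for the plan's rule. The simulation standard error at 5% is √(0.05 × 0.95 / 2,000) = 0.5 points, so these rates are compatible with the nominal level.

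**The case against.** The strongest defense is that the rule does what it says. When a predictor of enrollment is visibly imbalanced, it gets adjusted for, and the second condition keeps irrelevant variables out. The models are also not otherwise bare, since center, possibly time, and the primary covariates enter by other routes. The first-line comparisons for Secondary Aims 2 and 2a are bivariate, so the screen governs only multivariable models within secondary aims. All of this stands and limits the impact. It does not justify the screen: a small imbalance in a strong predictor can matter more than a significant one in a weak predictor, and the rule ignores the first.

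A reader might go further and infer that selecting the model this way invalidates the nominal p-values. The simulation does not support that; type I error stayed near 5%. Nor are the 30% to 37% figures the probability that the fitted model changes, because they leave out the enrollment condition.

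Two further cautions are fair. The power gains concern the incentive main effect under assumed inputs; nothing was shown for the non-inferiority interaction tests. In logistic models the benefit of adjustment is also not simply a smaller standard error: the conditional odds ratio changes and power can rise.

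Finally, imbalance is chance only for characteristics fixed before randomization. Phone answers are given after the incentive is disclosed, and the plan hypothesizes that incentives raise perceived risk. Attitude and risk items could therefore differ by arm because of the incentive, and an undefined covariate pool could let the screen pick them. That is a further reason to name the set.

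**Conclusion.** The point holds as a fault of specification and efficiency. Beyond center, a conditional time term and the primary covariates, RETAIN adjusts only for covariates that pass both conditions. At an assumed 0.05 threshold a strong predictor of enrollment is dropped about 95% of the time, so the planned adjustment is nearly equivalent to none, and which conditional odds ratio is estimated depends on chance. The illustrative cost is 2.6 to 11.4 points of power for the incentive main effect. Its direction was the same in all six scenarios, but its size rests on the assumed N, intercept and effects.

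The documents do not support a claim of inflated type I error, or a claim that RETAIN adjusts for nothing else. The main trial's primary aims are unaffected.

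**What to change.** Amend the RETAIN Analytic Strategy as follows:

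- Delete the arm-significance screen. Name a short set of covariates expected to predict enrollment, for example age, gender, education and prior research participation, and include them whatever the observed balance.
- Add the phone screener, because it stratified the randomization, and say how center is handled alongside it. If each screener works at one site, screener indicators already determine center, so the two should not both be entered as unrestricted fixed effects.
- Keep household income and economic well-being in their separate inducement models. Adding income to every model would undo the plan's own provision against collinearity.
- Leave research-attitude and risk-perception items, which are answered after incentive disclosure, out of the general adjustment set. Risk perception keeps its planned role in the undue-inducement model.

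The cost is SAP wording. The phone questionnaires already collect demographics, finances and previous research experience from randomized callers. The plan does not itemize the phone demographics and takes some items from main-trial forms where possible, so confirm that each named covariate is collected by phone and is available for callers who never enroll.
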